10.2.8.1 Imputation Methods of Rutherford Results for the ITT Population

For subjects without the efficacy endpoint (Rutherford Classification change from baseline to any post baseline result), the following imputation methods will be applied:

- For missing Baseline Rutherford Classification, assign the Rutherford Classification score at Screening if the Rutherford Classification score score at Day 0 is missing.
- For any post baseline Rutherford Classification, assign the post baseline Rutherford Classification score prior to the missing post baseline Rutherford Classification via the last observation carried forward (LOCF) method.

For subjects who had a major amputation or limb procedure carried out, the following imputation methods will be applied:

- For subjects with a major amputation, assign the Rutherford Classification score prior to the amputation.

- For subjects with a limb salvage, assign the Rutherford Classification score prior to the intervention.

10.3. Baseline Values

Unless specified otherwise, the baseline value for each variable is the last non-missing value recorded at the last visit on or before start of dosing. In most cases, baseline values are expected to be based on the assessment collected at the Day 0 (Pre-Dose) visit.

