4.2.7. VISUAL ANALOG SCALE (VAS) SCORE

Pain will be measured using the visual analog scale (VAS) at screening, before the first treatment (injection) on Day 0, pretreatment on Days 14, 28 and 42, Day 90, 6 months, 9 months and 12 months. The VAS scoring instrument is a 10-cm line, oriented horizontally, with the left end indicating “no pain” and the right end representing “pain as bad as it can be”. The patient is asked to mark a place on the line corresponding to the current pain intensity. The distance along the scale is then converted into a numeric reading as detailed in the study manual.

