4. SAMPLE SIZE JUSTIFICATION

The sample size for this Phase 2 study was chosen to estimate effect sizes and variability for a pivotal study. Assuming a standard deviation for change in VAS scores of 25, a mean change of 30 in the high dose group, 28 in the low dose group, and 10 in the placebo group, an Analysis of Variance (ANOVA) F-test at alpha of 5%, a sample size of 20:20:10 for high dose, low dose and placebo, respectively, will have 49% power to detect an overall difference among treatment groups.

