10.1.2. Imputation Methods of VAS Results for the ITT Population

In order to include all subjects in the ITT population, the following imputation rules will be applied for analysis of the ITT population.

For subjects without the primary efficacy endpoint (VAS change from baseline to 9 months), the following imputation methods will be applied:

- For missing Baseline VAS, assign the VAS score at Screening if the VAS score at Day 0 is missing.
- For missing 9 month VAS, assign the 12 month VAS score if the 9 month VAS is missing.

- For missing 9 month VAS, assign the last reported VAS prior to the 9 month VAS visit if both the 9 month and 12 month VAS assessments are missing.

For subjects who had a major amputation or limb procedure carried out, the following imputation methods will be applied:

- For subjects with a major amputation, assign the post baseline VAS score prior to the amputation.
- For subjects with a limb salvage, assign the post baseline VAS score prior to the intervention.

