10.2.2. TRANSCUTANEOUS OXYGEN PRESSURE ASSESSMENT (TcPO₂, MMHG)

Transcutaneous oxygen pressure measurements (tissue oxygenation) will be measured at the anterior calf, posterior calf, dorsum foot and chest. TcPO₂ measurements and change from baseline (= post-treatment – baseline) for each body region will be summarized by study visit and treatment arm using the method for continuous variables. The baseline value is the measurement taken at the Day 0 (Pre-Dose) Visit if the percent difference ($=|Day\ 0 - Screening|/Screening \times 100\%$) between the measurements taken at the Screening Visit and the Day 0 Visit is $\leq 15\%$. Otherwise, the baseline value is the average of the measurements taken at Screening and Day 0 Visits.

Additionally, TcPO₂ ratio for each of the body region (anterior calf, posterior calf, and dorsum foot) to chest will be calculated for each subject as TcPO₂ at each body region divided by the TcPO₂ at chest. The chest value to be used as the denominator when generating the TcPO₂ ratio for each of the body region will be by subject and calculated by taking the average of that subject's non-missing chest results reported at Day 0, Day 180, Day 270 and Day 365. Note: based on clinical input, chest values of less than 30 mmHg and greater than 95 mmHg should not be used for the purpose of assigning chest value averages. Therefore, such values will not be considered for TcPO₂ ratio determination. Supplemental analyses using such values may be generated for exploratory purposes. The change in the TcPO₂ ratio from baseline will also be calculated. The TcPO₂ ratio and the change in TcPO₂ from baseline will be summarized by study visit and study arm using the method for continuous variables.

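### The Screening pain VAS goes unused in the primary analysis; entering it with the Day 0 VAS as covariates would be a cheap efficiency gain

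*SAP*

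**What the plan says.** Protocol 4.2.7 provides two pre-treatment readings: "Pain will be measured using the visual analog scale (VAS) at screening, before the first treatment (injection) on Day 0". Each is one mark on a 10-cm line for pain at that moment.

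SAP 10.3 takes the last non-missing pre-dose value as baseline unless another rule is given: "In most cases, baseline values are expected to be based on the assessment collected at the Day 0 (Pre-Dose) visit". SAP 10.1 gives VAS no other rule. SAP 10.1.2 brings Screening in only as a substitute: "assign the VAS score at Screening if the VAS score at Day 0 is missing". The primary model in SAP 10.1 is a one-way ANOVA of change, with treatment as the only factor.

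SAP 10.2.2 treats TcPO2 differently. Day 0 alone is the baseline when the two readings differ by 15% or less. "Otherwise, the baseline value is the average of the measurements taken at Screening and Day 0 Visits". SAP 10.2.3 applies the same conditional rule to ABI and TBI.

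**The concern.** A single mark of momentary pain is noisy. In an unadjusted change-score analysis, all the noise in the Day 0 reading enters the primary outcome. A second pre-dose reading is already in the database and could absorb part of it. The SAP accepts Screening as baseline information for three secondary measures when the readings disagree, but gives no such rule for the primary endpoint and no reason for the difference. At stake is precision in a trial of 50 whose planned F-test has less than even power on its own inputs.

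**Working it through.** **Inputs from SAP 4.** The expected improvements are "a mean change of 30 in the high dose group, 28 in the low dose group, and 10 in the placebo group". The SD of the change is taken as 25, the arms hold 20, 20 and 10 patients, the overall test is an F-test at the 5% level, and the stated power is 49%.

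**Plan's own figure.** The weighted grand mean is (20×30 + 20×28 + 10×10)/50 = 25.2. The between-group sum of squares is 20(4.8)² + 20(2.8)² + 10(15.2)² = 2928. The noncentrality is 2928/625 = 4.685. With 2 and 47 df, power is **45.1%**, not 49%. Using the unweighted mean (22.67) gives noncentrality 5.198 and 49.3%, which is probably where the printed figure comes from. I use 45.1% as the reference.

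**Assumed, because the documents give no VAS correlations.** Let d be the correlation of Day 0 with Month 9, s that of Screening with Month 9, and r that of Screening with Day 0. Assume the same variance σ² at each visit. The printed SD fixes 2σ²(1 − d) = 625, so d = 0.5 gives σ² = 625.

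**Variance under each analysis** (noncentrality is 2928 divided by it):

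- Planned, change from Day 0: 2σ²(1 − d).
- Change from the mean of both readings: σ²[1 + (1 + r)/2 − d − s]. This is below the planned variance only if d − s < (1 − r)/2.
- Change from Day 0 with Day 0 as covariate: σ²(1 − d²). Its ratio to the planned variance is (1 + d)/2, which never exceeds 1.
- Change from Day 0 with both readings as covariates: σ²(1 − R²), where R² = (d² + s² − 2dsr)/(1 − r²).

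**Results at d = 0.5.** Planned power is 45.1% throughout. Day 0 as sole covariate gives residual SD 21.65 and power 57.3% throughout.

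| r | s | SD, averaging | Power, averaging | Residual SD, both covariates | Power, both covariates (45 df) |
|---|---|---|---|---|---|
| 0.5 | 0.5 | 21.65 | 57.3% | 20.41 | 62.6% |
| 0.6 | 0.45 | 23.05 | 51.8% | 21.14 | 59.4% |
| 0.7 | 0.5 | 23.05 | 51.8% | 21.00 | 60.0% |
| 0.7 | 0.45 | 23.72 | 49.4% | 21.37 | 58.4% |
| 0.8 | 0.5 | 23.72 | 49.4% | 21.25 | 58.9% |
| 0.8 | 0.4 | 25.00 | 45.1% | 21.65 | 57.2% |
| 0.8 | 0.3 | 26.22 | 41.5% | 21.25 | 58.9% |

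Worked example, r = 0.8 and s = 0.3. Averaging gives 625 × (1 + 0.9 − 0.5 − 0.3) = 687.5, so SD 26.22, a loss. Both covariates give R² = (0.25 + 0.09 − 0.24)/0.36 = 0.278 and variance 625 × 0.722 = 451, so SD 21.25.

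In the first row all correlations are equal, and averaging cuts the variance by 25% whatever their common value. By simulation, Dunnett power for at least one dose then rises from 52.4% to 64.3%.

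**Sensitivity to d.** With Day 0 as sole covariate, power is about 64% at d = 0.3 and about 52% at d = 0.7.

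The covariate figures assume covariates balanced across arms. Chance imbalance costs a little more. All figures assume 50 patients analysed; the per-protocol set needs a Month 9 VAS, so it may be smaller.

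**The case against.** The strongest reply is that nothing here is wrong. A last-pre-dose baseline is prespecified, unbiased and consistent with Protocol 3.2, which lists VAS among the measures repeated before the first injection. The primary objective is safety (SAP 2.1), and SAP 4 says the size was chosen to estimate effects and variability for a pivotal study, not to reach a power target. All of this stands, and it limits the point to efficiency.

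A reader might infer three stronger things that the documents do not support:

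- That the SAP always averages for TcPO2, ABI and TBI. It does so only when the readings differ by more than 15%, so there is no unconditional precedent.
- That Screening VAS is thrown away. It is kept as the fallback.
- That averaging would raise power at no cost. The two pre-dose readings are at most 60 days apart (Protocol 3.2; 30 in SAP Table 2), so they may well correlate more strongly with each other than either does with Month 9. That shrinks the gain. If Screening also tracks Month 9 clearly less well than Day 0 does, the gain vanishes or reverses.

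On selection, no entry criterion sets a VAS threshold, but rest pain is one route to eligibility and is judged at Screening. Randomisation protects the comparison between arms. It does not protect the within-arm paired tests in SAP 5.2 from regression to the mean, which is a reason not to move their baseline towards Screening.

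Most of the attainable gain needs only the Day 0 reading as a covariate. That is correct, and it shapes the fix.

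**Conclusion.** The point holds as an efficiency improvement. The primary model ignores pre-dose information that is already collected. Plain averaging is not a dependable remedy: from 45.1%, power goes to between 41.5% and 57.3% over the correlations tried, and averaging helps only if d − s < (1 − r)/2. Covariate adjustment is dependable. At d = 0.5 it gives 57.3% with Day 0 alone. With both readings it gives about 57-60% when the pre-dose pair is the more closely correlated, and 62.6% when all correlations are equal. Screening therefore adds about 0-5 points to the roughly 12 gained from Day 0. Apart from one degree of freedom and chance imbalance, adding Screening cannot do worse than Day 0 alone as covariate. The sizes rest on the SAP's SD and means, equal variance across visits, and assumed correlations.

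**What to change.** Before unblinding, amend SAP 10.1 and 10.3:

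- Keep change from Day 0 to Month 9 as the endpoint.
- Add Day 0 VAS and Screening VAS as covariates beside treatment, with the Dunnett comparisons made on the adjusted means.
- If one pre-dose score is missing, use the other in its place.
- Keep the unadjusted Day 0 ANOVA as a sensitivity analysis.
- State whether the percent-change and subgroup models take the same covariates.

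The analysis-model footnotes of the VAS table shells (Tables 5.1.1, 5.2.1 and 5.3.1.1 and their counterparts) need matching edits. No new data are needed. The costs are two degrees of freedom and reliance on a Screening reading that may be up to 60 days old, or 30 by SAP Table 2.

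If averaging is preferred instead, the Baseline entry in the SAP definitions and the shells' baseline footnotes must change too, and Day 0 alone should be kept for the within-arm paired tests.

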10.4. Multiplicity Adjustments

Pairwise comparisons using Dunnett's test adjust for multiple comparisons. Otherwise, there will be no adjustments for multiple comparisons or interim analyses.

11. SAFETY ANALYSES

All subjects who received study drug will be included in the safety analyses, analyzed according to the study treatment actually received.

11.1. Study Drug Exposure

Study drug exposure will be summarized descriptively by treatment arm for Day 0, Day 14, Day 28 and Day 42. Categorical variables to be summarized using counts and percentages include "Was dose administered?" (Yes, No), the zone of the dose administration (I, II, III, IV) and "Was the total volume (8 mL) administered?" (Yes, No). In addition, the elapsed time of study drug administered (continuous variable) will be summarized in minutes using descriptive statistics.

11.2. Adverse Events

All adverse event summaries will be restricted to Treatment Emergent Adverse Events (TEAE), which are defined as those AEs that occurred on or after first dosing date and those existing AEs that worsened during the study. Verbatim terms on case report forms

will be mapped to preferred terms and system organ classes using the MedDRA dictionary (version 14.0).

Each adverse event summary will be displayed by treatment arm. Summaries that are displayed by system organ class and preferred terms will be ordered by descending order of incidence of system organ class and preferred term within each system organ class. The number of subjects experiencing a particular event, the percentage of subjects experiencing the event will be presented. The total number of events will be presented for a select set of summaries. The following summaries will be created:

- TEAE by MedDRA system organ class and preferred term;
- TEAE by MedDRA system organ class, preferred term, and maximum severity. At each level of subject summarization a subject is classified according to the highest severity if the subject reported one or more events. AEs with missing severity will be considered severe for this summary;
- TEAE by MedDRA system organ class, preferred term, and closest relationship to study drug (Related/Unrelated). At each level of subject summarization a subject is classified according to the closest relationship if the subject reported one or more events. AEs with a missing relationship will be considered related for this summary; Events classified as ‘possibly’, ‘probably’ or ‘definitely’ will be considered ‘related’;
- Serious TEAEs by MedDRA system organ class and preferred term.

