18. Subjects requiring > 81 mg daily of acetylsalicylic acid; If > 81 mg are taken at screening, subjects may be enrolled if willing/able to switch to another medication for the duration of the study;
19. Subjects requiring regular COX-2 inhibitor drug(s) or high dose steroids (excepting inhaled steroids);
20. Major psychiatric disorder in past 6 months;
21. History of drug or alcohol abuse / dependence in the past 2 years;
22. Use of an investigational drug or treatment in past 12 months; concurrent participation in investigational protocol or unapproved therapeutics; and
23. Unable or unwilling to give informed consent.

STUDY PROCEDURES

Patients will be screened for study eligibility after giving informed consent. Screening should occur within the 60 days prior to Day 0 (day of injection). Screening will include assessment of study eligibility, a complete medical history, physical exam, cancer screening tests, viral screening, ABI & TBI, TcPO₂, VAS, 12 lead EKG, retinal fundoscopy, clinical chemistry, hematology, urinalysis, and pregnancy test (women of childbearing potential only), and documentation of any ulcers or gangrenous areas.

Patients will be treated with a final dose of 8 mg VM202, 16 mg VM202 or placebo by intramuscular injections in the affected calf on Day 0, Day 14, Day 28 and Day 42. VM202 will be delivered in a solution of 0.5 mg VM202 / mL.

TREATMENT GROUP	FINAL DOSE VM202	DOSE VM202 (MG) PER VISIT			
		DAY 0	DAY 14	DAY 28	DAY 42
Low Dose	8 mg	4	4	0	0
High Dose	16 mg	4	4	4	4
Placebo	0	0	0	0	0

Patients in the Low Dose Group (8 mg VM202) will receive:

- Day 0: 4 mg of VM202 (16 injections of 0.5 ml of VM202)
- Day 14: 4 mg of VM202 (16 injections of 0.5 ml of VM202)
- Day 28: Placebo only (16 injection of 0.5 ml normal saline)
- Day 42: Placebo only (16 injection of 0.5 ml normal saline)

Patients in the High Dose Group (16 mg VM202) will receive:

-
- Day 0: 4 mg of VM202 (16 injections of 0.5 ml of VM202)
 - Day 14: 4 mg of VM202 (16 injections of 0.5 ml of VM202)
 - Day 28: 4 mg of VM202 (16 injections of 0.5 ml of VM202)
 - Day 42: 4 mg of VM202 (16 injections of 0.5 ml of VM202)

Patients in the placebo control group will receive 16 injections of 0.5 ml normal saline at each visit.

Determination of HGF serum levels will be made immediately pre-treatment on Day 0, immediately pre-treatment on Day 42, Day 49 and Day 90.

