6.2.3. SAFETY

Any patient who receives VM202 will be included in the safety analysis population. Adverse events (including serious adverse events, and adverse events leading to treatment discontinuation) throughout the 12 month follow-up will be described according to severity and to their relationship with the study drug and / or device and procedure. Descriptive statistics (N, mean, median, SD, minimum and maximum values, where applicable) will be used to characterize safety parameters.

All patients will all undergo testing as presented in the American Cancer Society Cancer Screening Guidelines as part of their baseline testing to rule out cancer.

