Appendix 4. Test Article Administration

1. *Test article preparation*

VM202 - VM202 is supplied in a sterile glass vial containing 2.2 mg of lyophilized study product. Before administration, it will be reconstituted with 4.4 mL of water for injection (WFI) for a final VM202 concentration of 0.5 mg / mL. Each reconstituted vial is only to be used for one subject. For the Low Dose treatment arm, the final doses of 8 mg of VM202 will be divided evenly between the Day 0 administration and the Day 14 administration, with the Day 28 and Day 42 injections consisting of normal saline (see description of normal saline below). The High Dose treatment arm will receive final doses of 16 mg of VM202 divided evenly between the Day 0, Day 14, Day 28 and Day 42 administrations. Individual injections will be 0.5 mL. All injections will be 0.5 mL administered by intramuscular injections.

Placebo - Patients assigned to either the placebo arm or the Low Dose arm will receive normal saline injections. The placebo group will receive only normal saline injections; the Low Dose arm will receive VM202 for the first two injection procedures (Day 0 and Day 14), and then normal saline for the next two injection visits (Day 28 and Day 42). Visually, normal saline is indistinguishable from reconstituted VM202.

Table 3. Single dose preparation and delivery, Day 0 and Day 14

TREATMENT ARM	NUMBER OF VIALS RECONSTITUTED	TOTAL VOLUME TO BE INJECTED	NUMBER OF INJECTIONS	VOLUME / SINGLE INJECTION
Low Dose 8 mg VM202	2 Vials VM202, reconstituted with WFI	8 mL	16	0.5 mL
High Dose 16 mg VM202	2 Vials VM202, reconstituted with WFI	8 mL	16	0.5 mL
Placebo – Normal Saline	NA	8 mL	16	0.5 mL

Table 4. Single dose preparation and delivery, Day 28 and Day 42

TREATMENT ARM	NUMBER OF VIALS RECONSTITUTED	TOTAL VOLUME TO BE INJECTED	NUMBER OF INJECTIONS	VOLUME / SINGLE INJECTION
Low Dose 8 mg VM202	NA – Normal Saline	8 mL	16	0.5 mL
High Dose 16 mg VM202	2 Vials VM202, reconstituted with WFI	8 mL	16	0.5 mL
Placebo – Normal Saline	NA	8 mL	16	0.5 mL

2. **Test material administration** – Patients will receive injections of VM202 or placebo on Day 0, Day 14, Day 28, and Day 42. A fine needle (e.g. 27 gauge, 1”) suitable for IM injections will be used. Only one leg will be treated in this study. Distribute injection sites evenly over the calf muscle, carefully avoiding fascia.

-

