Note: At each level of summation (overall, system organ class, preferred term), subjects reporting more than one adverse event are counted only once using the highest severity.
path\t_program.sas date time

Table 16
Treatment Emergent Adverse Events by Relationship to Study Drug
Safety Population

System Organ Class / Preferred Term	Placebo (N=)		VM202- 8 mg (N=)		VM202- 16 mg (N=)	
	Related ^[1]	Unrelated ^[2]	Related ^[1]	Unrelated ^[2]	Related ^[1]	Unrelated ^[2]
Subjects Reporting at Least One Adverse Event	n (%)	n (%)	n (%)	n (%)	n (%)	n (%)
System Organ Class 1	n (%)	n (%)	n (%)	n (%)	n (%)	n (%)
Preferred Term 1	n (%)	n (%)	n (%)	n (%)	n (%)	n (%)
Preferred Term 2	n (%)	n (%)	n (%)	n (%)	n (%)	n (%)
System Organ Class 2	n (%)	n (%)	n (%)	n (%)	n (%)	n (%)
Preferred Term 1	n (%)	n (%)	n (%)	n (%)	n (%)	n (%)
Preferred Term 2	n (%)	n (%)	n (%)	n (%)	n (%)	n (%)

Note: At each level of summation (overall, system organ class, preferred term), subjects reporting more than one adverse event are counted only once using the closest relationship to study drug.

^[1] Includes all events reported as "Possibly," "Probably," "Definitely" or with missing relationship to study drug.

^[2] Includes all events reported as "Not Related" relationship to study drug.

path\t_program.sas date time

Table 17
Treatment Emergent Serious Adverse Events by System Organ Class and Preferred Term
Safety Population

System Organ Class / Preferred Term	Placebo (N=)		VM202- 8 mg (N=)		VM202- 16 mg (N=)	
	Number of Subjects ^[1]	Number of Events	Number of Subjects ^[1]	Number of Events	Number of Subjects ^[1]	Number of Events
Subjects Reporting at Least One Serious Adverse Event	n (%)	n	n (%)	n	n (%)	n
System Organ Class 1	n (%)	n	n (%)	n	n (%)	n
Preferred Term 1	n (%)	n	n (%)	n	n (%)	n
Preferred Term 2	n (%)	n	n (%)	n	n (%)	n
System Organ Class 2	n (%)	n	n (%)	n	n (%)	n
Preferred Term 1	n (%)	n	n (%)	n	n (%)	n
Preferred Term 2	n (%)	n	n (%)	n	n (%)	n
Etc.						

^[1] At each level of summation (overall, system organ class, preferred term), subjects reporting more than one adverse event are counted only once.
path\t_program.sas date time

Table 18
Hematology - Shift from Baseline
Safety Population
Analyte #1

Time Point	Baseline ^[1]								
	Placebo (N=)			VM202- 8 mg (N=)			VM202- 16 mg (N=)		
	High	Normal	Low	High	Normal	Low	High	Normal	Low
Day 14									
High	n (%)	n (%)	n (%)	n (%)	n (%)	n (%)	n (%)	n (%)	n (%)
Normal	n (%)	n (%)	n (%)	n (%)	n (%)	n (%)	n (%)	n (%)	n (%)

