Programmer note sort by assessment date within each subject.

Listing 26
Rutherford Classification

Treatment Group	Subject ID	Visit	Date of Assessment (Study Day)	Rutherford Classification	Comments
Placebo	xxxxxx	visit	date9. (xx)		
		visit	date9. (xx)	x	comments
				...	comments
VM202- 8 mg	xxxxxx	visit	date9. (xx)	x	comments
		visit	date9. (xx)	x	comments
				...	comments
VM202- 16 mg	xxxxxx	visit	date9. (xx)	x	comments
		visit	date9. (xx)	x	comments
				...	comments

Note: Scale for Rutherford Classification-

0= Asymptomatic - No hemodynamically
1= Mild Claudication
2= Moderate Claudication
3= Severe Claudication
4= Ischemic Rest Pain

5= Minor Tissue Loss - Non-healing ulcer, focal gangrene with diffuse pedal ischemia

6= Major Tissue Loss - Extending above the TM level, functional foot no longer salvageable

Note: Study Day = [(Date of Event) - (Treatment Start Date)]; 1 is added to the difference when 'Date of Event' is greater than or equal to 'Treatment Start Date'.
path\t_program.sas date time

Programmer note sort by date of assessment within each subject

Listing 27
Study Drug Administration

Treatment Group	Subject ID	Visit Date (Study Day)	Was a Dose Administered?	Study Leg Assignment	Kit #	Start Time of First Injection	Stop Time of Last Injection	Was Total Volume (8mL) Administered?	Reason Total Volume Not Administered	Total Volume Administered (mL)	Injection Zones
						If No,					
Placebo	xxxx	Date9.	Yes/No	left/right	xxxx	time5.	time5.	Yes/No	xxxxxx	xx	I/II/II/IV
	xxxx	Date9.	Yes/No	left/right	xxxx	time5.	time5.	Yes/No	xxxxxx	xx	I/II/II/IV
VM202- 8 mg	xxxx	Date9.	Yes/No	left/right	xxxx	time5.	time5.	Yes/No	xxxxxx	xx	I/II/II/IV
	xxxx	Date9.	Yes/No	left/right	xxxx	time5.	time5.	Yes/No	xxxxxx	xx	I/II/II/IV
VM202- 16 mg	xxxx	Date9.	Yes/No	left/right	xxxx	time5.	time5.	Yes/No	xxxxxx	xx	I/II/II/IV
	xxxx	Date9.	Yes/No	left/right	xxxx	time5.	time5.	Yes/No	xxxxxx	xx	I/II/II/IV
...											

Note: Study Day = [(Date of Event) - (Treatment Start Date)]; 1 is added to the difference when 'Date of Event' is greater than or equal to 'Treatment Start Date'.
path\t_program.sas date time

Programmer note sort by visit date within each subject

Listing 28
Adverse Events

Treatment Group	Subject ID	AE #	Adverse Event// Preferred Term	Start Date (Study Day)	End Date (Study Day)	Severity	Treatment	Study Drug Action	Relationship To Study Drug	Relationship To Procedure	Relationship To Underlying Disease	Outcome	Serious?

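### Procedure-related adverse events, and those leading to treatment discontinuation, are listed but not tabulated, and Table 16 can class an injection-related event as Unrelated

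*SAP*

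**What the plan says.** Protocol 6.2.3 (repeated in the synopsis) sets the commitment. It covers all adverse events over the follow-up year, naming serious ones and those that cause a patient to stop treatment, and says that they "will be described according to severity and to their relationship with the study drug and / or device and procedure". Protocol 5.2 has the site record each event's relationship to study medication, injection procedure and/or underlying disease. Protocol 5.2.1 defines four causality grades. Each is worded for the product or the way it is administered, taken together.

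SAP 11.2 restricts reporting to treatment-emergent events (TEAEs) and lists the summaries to be created: by system organ class and preferred term (Table 14), by maximum severity (Table 15), "TEAE by MedDRA system organ class, preferred term, and closest relationship to study drug (Related/Unrelated") (Table 16), and serious TEAEs by class and term (Table 17). The footnote to Table 16's Unrelated column reads "Includes all events reported as 'Not Related' relationship to study drug". Possible, probable, definite and missing ratings count as Related.

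The procedure rating survives in Listings 28 and 29, which have a separate column headed "Relationship To Procedure" and another for the action taken with study drug.

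**The concern.** The protocol names two things that the SAP's summary tables do not deliver: causality with respect to the procedure, and events that led to stopping treatment. SAP 11.2 gives no reason for the omission, although the neighbouring items in the same protocol sentence (severity, drug relationship, serious events) all became tables.

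The omission matters because SAP 2.1 makes the safety of giving VM202 intramuscularly the primary objective, and the injections are part of that. The protocol treats local harm as a real possibility: its injection-reaction grading (4.2.12, Table 2) extends to ulceration, necrosis and operative intervention, and its preclinical section names mild, transient injection-site irritation as the only toxicity seen. Someone who reads Table 16's Unrelated column with the Protocol 5.2.1 definitions in mind would take it to exclude injection-related events. By its footnote, it does not.

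**Working it through.** The plan states no figure on this point, so the check sets the passages side by side.

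**Step 1. Commitment against output.**

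| Item in Protocol 6.2.3 | SAP table | Other SAP coverage |
|---|---|---|
| Severity | Table 15 | Listings 28, 29 |
| Relationship to study drug | Table 16 | Listings 28, 29 |
| Relationship to procedure | None | Listings 28, 29; Table 22 in part |
| Serious events | Table 17, with no split by relationship | Listing 29 |
| Events leading to treatment discontinuation | None | Listings 28, 29; Table 1 in part |

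The partial coverage has these limits:

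- Table 22 (SAP 11.6) is a Yes/No count of injection site reactions by arm and visit. It ends at Day 49 and shows no grade. It does not cover other procedure-related events, or later ones, in the 12-month follow-up.
- Table 1 gives the primary reason for leaving the study, with an adverse-event row. A patient who stops injections because of an event but stays in follow-up is not counted there. Table 13 shows whether each dose was given, without a reason.
- Listings 28 and 29 are subject-level lines, with no counts or percentages by arm.

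**Step 2. How Table 16 classes an event**, from SAP 11.2 and the table footnotes:

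| Drug rating | Procedure rating | Class in Table 16 |
|---|---|---|
| Possible, probable or definite | Any | Related |
| Missing | Any | Related |
| Not related | Not related | Unrelated |
| Not related | Possible, probable or definite | Unrelated |

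The last row is the problem. Table 16 counts each subject once per level, by closest relationship. Such an event therefore puts the subject in the Unrelated column only if that subject has no drug-related event at the same level.

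**Step 3. Can the last row occur?** The separate columns in Listings 28 and 29 allow it. Protocol 5.2.1, read literally, pulls the other way: its lowest grade denies a link with either the product or its administration, so an injection-caused event would not qualify for it. Neither document says how the joint wording maps to the two ratings. The last row is possible, but its frequency is undetermined.

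**Step 4. Exposure.** Inputs: "Patients in the placebo control group will receive 16 injections of 0.5 ml normal saline at each visit" (Protocol, study design) and "Patients will receive injections of VM202 or placebo on Day 0, Day 14, Day 28, and Day 42" (Protocol Appendix 4). The active arms have the same number per visit.

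- Injections per full course: 16 × 4 = 64, in one calf, in every arm.
- Volume per visit: 16 × 0.5 mL = 8 mL, which agrees with SAP 11.1.

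This measures exposure, not affected events. The documents give no rate of procedure-related events, so the number misplaced cannot be calculated.

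**The case against.** The strongest reply is that nothing is lost. Table 14 counts every TEAE by arm whatever its cause, Table 15 gives severity and Table 17 gives all serious events. Table 16 is titled by relationship to study drug and shows exactly that. Every arm has the same injection schedule, so the comparison of VM202 with placebo in Table 14 needs no attribution. The protocol says that events will be described and specifies no tables; in a trial of 50 patients, listings can be read line by line.

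Much of this stands. The drug-versus-placebo comparison is unaffected, and no event disappears. But identical injections in every arm also mean that no between-arm contrast can show what the injections do. The investigator's procedure rating is then the main tool, and it is never summarised. A listing describes individual events but gives no rate by arm.

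A reader might infer that all injection-caused events will be reported as Unrelated. The documents do not support that: the joint grades in Protocol 5.2.1 may lead investigators to rate such events as related, and missing ratings count as related. Nor do they support saying that the SAP ignores the procedure or discontinuation altogether, given Listings 28 and 29, Table 22 and Table 1.

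**Conclusion.** The gap is real and limited. Two items named in Protocol 6.2.3, relationship to procedure and events leading to treatment discontinuation, have no summary table, and serious events have no tabulated relationship of any kind. Table 16 can class an event rated related to the injections but not to the drug as Unrelated.

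The number of such events cannot be computed. It depends on how investigators apply the joint wording of Protocol 5.2.1 to separate ratings and on a procedure-related event rate that the documents do not give. The conclusion assumes that the listing columns reflect separate ratings on the case report form, as their layout indicates. It concerns the completeness and labelling of safety reporting and does not touch the efficacy analysis. It is still worth correcting, because the primary objective is the safety of intramuscular administration and the data will already be in hand.

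**What to change.** In SAP 11.2 and the matching table layouts:

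1. Keep Table 16 as the drug-relationship table, but label its second column as not related to study drug.
2. Add summaries of TEAEs and of serious TEAEs by relationship to the injection procedure. Show drug and/or procedure as a further row that does not replace the drug-only row, so that the drug signal is not blended with a procedure common to all arms.
3. Add a table of TEAEs leading to discontinuation of study treatment, by class, term and arm, from the study-drug-action field in Listings 28 and 29.
4. State how the joint causality definitions in Protocol 5.2.1 apply to the separate drug and procedure ratings.

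The cost is a few extra tables and a short clarification, with no new data collection. The reported rate of treatment-related events may rise once procedure-related events are shown.
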